**Table 1. IRC005 study days and analysis windows**

	Days since randomization						
Visit	Day 0 (Baseline)	Day 1	Day 2	Day 3	Day 7	Day 14	Day 28
Per protocol (Days)	0	1	2	3	7±1	14±2	28±3
Analysis (Days)	0	1	2	3-4	5-9	10-18	22-36

## **4. Analysis Populations**

All tables and figures will note the analysis population used:

- Enrolled Population includes all subjects who had a signed informed consent form for screening.
- Modified Intention To Treat (mITT) Population includes all subjects who were randomized and who had the study plasma infusion started (as defined in Section 12.1 of the protocol).

## 5. Study population

### 5.1 Screening, screen failures, and exclusion of subjects (Enrolled Population)

The purpose of this section is to describe the number enrolled (i.e. signed an informed consent form for screening), account for screen failures to give the number randomized, and then to account for exclusion of randomized subjects from subsequent analyses because they did not have infusion of study plasma started.

- a. Table: Number screened: overall and by month/year. Dates of first and last subjects screened.
- b. Table: Screen failures: Number by reason (including any due to screening eligibility violations).
- c. Table: Number randomized in each arm, showing number excluded from analysis population because they did not have a plasma infusion started.
- d. Table of demographic characteristics: Age at randomization and associated age group (adult versus child); sex; pregnancy status; self-reported NIH race/ethnicity (major category race, minor category ethnicity).
- e. List of reasons plasma infusion never started: Randomized arm, subject ID, site, age, sex, pregnancy status, reason (including reasons due to randomization eligibility violations), subject's study status (completed 28 days, died, discontinued early from study, reason for discontinuation). [Sort by randomized arm and subject ID].
- f. For enrolled subjects who were not randomized or who were randomized but did not receive plasma:
  - i. List of deaths: Subject ID, whether randomized or not (and randomized arm if randomized), site, age, pregnancy status, days from enrollment to death, primary cause of death. [Sort by subject ID].
  - ii. List of SAEs: Subject ID, whether randomized or not (and randomized arm if randomized), site, age, pregnancy status, days from enrollment to SAE, SAE (MedDRA SOC and PT, and verbatim description), ICH seriousness criterion met, severity grade, outcome. [Sort by subject ID, MedDRA SOC and PT].
- g. List describing deviations/violations of eligibility criteria (for screening or randomization): Randomized arm, subject ID, site, age, pregnancy status, deviation/violation, description of deviation/violation, subject's study status (completed 28 days, died, discontinued early from study, reason for discontinuation). [Sort by randomized arm and subject ID].

## 6. Baseline characteristics (mITT population)

Baseline characteristics are those recorded as Day 0; if values are missing but are available from screening assessments, then these will be used instead. Tables in this section will show number (%) for categorical variables, and median, 25th and 75th percentiles, min and max for the ordinal/continuous variables; number with missing values. No statistical comparison will be undertaken between randomized arms (instead, the impact of any imbalance may be evaluated in adjusted analyses—see efficacy analyses section).

- a. Table: Number randomized: overall and by month/influenza season (generally November – March, but for grouping will be August – July). Dates of first and last randomizations.
- b. Table: Number randomized by site.
- c. Table of demographic characteristics: Age at randomization and associated age group (adult versus child, with children classified as <2 years, ≥2 to <8 years, and ≥8 to <18 years); sex;

pregnancy status; self-reported NIH race/ethnicity (major category race, minor category ethnicity).

- d. Table of body mass index (BMI) and BMI group (adults only, using standard U.S. categories for underweight, etc.).
- e. Table of influenza disease status: Influenza vaccination in the current season; days from onset of influenza symptoms to randomization; influenza antivirals taken through to randomization (number (%)) for each specific drug or combination of drugs, and number (%) taking any antivirals); influenza status by site testing (negative versus positive, type of testing), influenza status from central lab from Day 0 (negative versus positive) and subtype from central laboratory testing; viral shedding in OP sample by qPCR at central laboratory testing.
- f. Table of days hospitalized prior to randomization
- g. Table of chronic medical conditions and allergies (defined as starting >30 days prior to randomization), by MedDRA SOC and PT.
- h. Table of vital signs, including SaO2.
- i. Table of clinical status: Study 6-point ordinal scale; measures of clinical support (hospitalization, oxygen requirement, mechanical ventilator requirement, ICU requirement, ECMO requirement), ARDS (yes/no, and by severity)
- j. Table of respiratory status: PaO2/ FiO2 Ratio, SpO2/ FiO2 Ratio [excluding those on ECMO as these criteria are erroneous in this population].
- k. Table of clinical status scores: NEW Score and SOFA Score for adults; PEW Score and PELOD Score for children.
- l. Table of chest X-ray findings (only reported if performed for clinical indications): Obtained: yes/no; if yes, % with each abnormal finding.
- m. Table of CBC results: White cell count and differential white cell count (neutrophil and lymphocyte percentages), hemoglobin, hematocrit, and platelets; PT and INR.
- n. Table of blood chemistry results: Creatinine, glucose, total protein, ALT/GPT, AST/GOT, total bilirubin.

## **7. Study Execution (mITT population)**

### **7.1 Study status of subjects and losses to follow-up.**

- a. Table: Number (%) for the following categories:
  - Completed Day 28 visit, categorized by whether at <25 days versus 25-31 days (protocol-specified window) versus >31 days
  - Died prior to completing Day 28 visit
  - Lost to follow-up before completing Day 28 visit (with subcategories showing reason for loss)
- b. List of subjects lost to follow-up before completing Day 28 visit showing: Randomized arm, days from randomization to last study visit, subject ID, site, age, pregnancy status, reason for loss [Sort by randomized arm, days from randomization, subject ID].

### **7.2 Anti-influenza plasma receipt**

[Note: Subjects who did not start study plasma are not included in analysis population].

- a. Table showing number (%) in following categories
  - Full planned treatment
  - Partial treatment
  - More than full planned treatment
- b. Table of HAI titers in plasma infused
- c. Table of plasma volumes.
  - Adults – combined volume for first and second unit.
  - Children – combined volume for first and second unit (of applicable) per kg body weight.
- d. For subjects who did not receive full planned treatment, or received more than full planned treatment: randomized arm, subject ID, site, age, pregnancy status, type of departure from full planned treatment (partial treatment versus more than full planned treatment), reason for not receiving full planned treatment. [Sort by randomized arm, subject ID].
- e. Table of hours from randomization to start of initial plasma infusion among those documented as having received one or more infusions: median, 25th and 75th percentiles, min and max, number (%) starting at >24 hours after randomization.
- f. Table of hours between first and second infusion among those documented as having received two or more infusions: median, 25th and 75th percentiles, min and max.
- g. Table: median, 25th and 75th percentiles, min and max (and sample size) for HAI titer in first infusion; and similarly for second infusion.
- h. Listing of subjects that received units that were not assigned by randomization including site, subject ID, randomized treatment arm, HAI titer in unit(s) received, ABO blood type, ABO of units received, and description of deviation

### **7.3 Use of influenza antivirals**

- a. Table of influenza antivirals taken between study enrollment and Day 28: number (%) for each specific drug or combination of drugs, and number (%) taking any antivirals (note: per protocol, subjects should be taking an antiviral).

## **8. Safety Endpoints (mITT Population)**

### **8.1 Mortality**

- a. List of deaths: Randomized arm, days from randomization to death, subject ID, site, age, pregnancy status, days from start of first infusion to death, whether or not death occurred in-hospital during initial admission, primary cause of death, relatedness to study intervention. List to include all deaths reported, irrespective of time from randomization to the date of death (i.e.

including any deaths reported after the Day 28 evaluation). [Sort by randomized arm, days from randomization to death and subject ID].

- b. Table: Number (%) dying during initial hospitalization; p-value from Fisher's Exact Test. The denominator for this analysis will be the number of subjects who have an infusion started (and so included in all analyses). A sensitivity analysis will be performed using the ITT population.
- c. Figure and analysis of mortality occurring between randomization and the date/time of the Day 28 evaluation: Kaplan-Meier plot of time from randomization to death (censoring at earlier of Day 28 evaluation if completed follow-up, or at date of last contact if lost to follow-up prior to Day 28 evaluation), with associated table showing: number censored, number dying; p-value from log-rank test. The estimated hazard ratio and associated 95% confidence interval comparing randomized arms will be obtained using a proportional hazards model applied to the times of death with censoring as above. For clarity, the date/time of the Day 28 evaluation for this analysis is defined to be the date/time of the Day 28 assessment of the 6-point clinical status. A death occurring on the same day as this Day 28 evaluation but after this date/time (or on a subsequent day) will not be included in this analysis (as reporting of such deaths is not required by the protocol). This also means that a death which is included in this statistical analysis which occurred on the day of the Day 28 evaluation should also show as the "result" of the Day 28 assessment of the 6-point clinical status.

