10.3.2 Serious Adverse Events

All SAEs (regardless of relationship and whether or not they are also UPs) must be reported on the Safety Expedited Report Form (SERF) and sent to the Clinical Safety Office (CSO) by fax or email attachment. Deaths and immediately life threatening SAEs must be reported to the CSO within 1 business day after the site becomes aware of the event. All other SAEs must be reported within 3 business days of site awareness.

CSO CONTACT INFORMATION:

Clinical Safety Office
[name]
[name]
[contact]
[contact]
E-mail: [contact]

SAEs that have not resolved by the end of the follow-up period are followed until final outcome is known. If it is not possible to obtain a final outcome for an SAE (e.g., the subject is lost to follow-up), the reason a final outcome could not be obtained will be recorded by the investigator on the AE eCRF and the SERF.

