## **10.3 Disposition**

- a. Table of disposition following initial hospitalization (home without assistance, home with home health care, rehabilitation, chronic nursing facility, initial hospitalization ongoing at 28 days, died during initial hospitalization): Number (%) of subjects in each disposition category, showing also number with missing values (eg due to withdrawal of consent during initial hospitalization). The table will also show the p-value comparing treatments (Wald test from the proportional odds model), as well as the estimated proportional odds ratio comparing treatments with associated 95% CI.

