## **10.4 Secondary endpoints: Hospitalization, intensive care/support and ARDS**

The protocol specifies the following secondary endpoints:

- Duration of initial hospitalization
- Duration of all hospitalizations
- Duration of admission to an ICU among those in an ICU at randomization
- Incidence of new ICU admission among those not in an ICU at randomization
- Duration of supplemental oxygen use among those requiring oxygen at randomization
- Incidence of supplemental oxygen use among those not requiring oxygen at randomization
- Duration of mechanical ventilation use among those requiring mechanical ventilation at randomization
- Incidence of new mechanical ventilation use among those not requiring mechanical ventilation at randomization

- Duration of ECMO use among those on ECMO at randomization
- Incidence of new ECMO use among those not on ECMO at randomization
- Duration of ARDS among those with ARDS at randomization
- Incidence of new ARDS among those not having ARDS at randomization

Notes:

- i. Each of these measures will be evaluated through to the Day 28 visit and so will reflect the use of interventions (or of ARDS) during the study follow-up period.
- ii. Deaths and losses to follow-up may affect the interpretation of the results for these endpoints (e.g. deaths, losses to follow-up). Sensitivity analyses may be undertaken to assess how the interpretation of formal analyses might be affected by these issues.

- a. Table showing durations of interventions: n (will be overall sample size for hospitalizations, and number receiving intervention at randomization for other interventions and ARDS), median, 25th and 75th percentiles and min, max. Difference in medians between treatments, p-value from Wilcoxon's test and associated 95% CI for difference.
- b. Table showing incident use of intervention (or new development of ARDS): n (will be number not receiving intervention or not having ARDS at randomization), number (%) with incident use of intervention (or new development of ARDS), difference in %'s between treatments, and odds ratio comparing treatments with p-value and associated 95% CI from exact logistic regression.

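### In-hospital mortality (SAP 8.1b) has no cut-off although systematic follow-up stops at the Day 28 visit; the other 28-day outcomes end on each subject's own visit date

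*SAP*

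**What the plan says.** In-hospital mortality during the initial hospitalization is a secondary objective (protocol 2.2; SAP Protocol Summary). SAP 8.1b analyses it as "Number (%) dying during initial hospitalization", compared by Fisher's exact test. It adds that "The denominator for this analysis will be the number of subjects who have an infusion started" and asks for an ITT sensitivity analysis. No last day is given. The listing in 8.1a takes in deaths reported at any time and flags those in hospital during the initial admission.

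The neighbouring rules do have an end:

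- SAP 8.1c analyses "mortality occurring between randomization and the date/time of the Day 28 evaluation" and leaves out later deaths, "as reporting of such deaths is not required by the protocol".
- SAP 8.2 tabulates all SAEs, then adds a second table that stops at the Day 28 visit.
- SAP 10.3 has separate disposition categories: "initial hospitalization ongoing at 28 days, died during initial hospitalization".
- SAP 10.4, note i: "Each of these measures will be evaluated through to the Day 28 visit".

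In the protocol, follow-up runs through Study Day 28 (3.1, 3.2) and AE and SAE reporting through the Day 28 visit (10.2). After that, two routes remain. Under 10.3.2, "SAEs that have not resolved by the end of the follow-up period are followed until final outcome is known". Under 10.4, a plasma-related SAE is reported if the site learns of it, but sites need not look for late events apart from pregnancy follow-up. Protocol 10.4 also says that SAEs after the Day 28 visit are noted in the report but not used in the main efficacy and safety analysis.

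**The concern.** A numerator open in time needs follow-up open in time. Here a subject in hospital at Day 28 stays in the 8.1b denominator and is counted as a survivor unless a later death reaches the database. Whether it does depends on an unresolved SAE or on a causality judgement plus the site's awareness. The Fisher test would then mix deaths that are completely ascertained up to the Day 28 visit with later ones that are not.

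Two tables could also disagree. A subject who dies in hospital on Day 40 can be an in-hospital death in 8.1b and an ongoing hospitalization in 10.3.

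A related, lesser issue is that the time-to-death analysis and the durations end at a visit and not on a day. Where the visit falls can decide whether a death near Day 28 counts, and how two subjects still on support are ranked.

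**Working it through.** **1. Rules side by side.** Take a subject still in the initial admission at a Day 28 visit held on Day 28, who dies in hospital on Day 40.

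| Place | Treatment of that death |
|---|---|
| SAP 8.1a | Listed if reported |
| SAP 8.1b | A death if reported, otherwise a survivor |
| SAP 8.1c | Excluded |
| SAP 8.2 | In the first SAE table if reported as an SAE; not in the second if onset was after the visit |
| SAP 10.3 | Hospitalization ongoing at 28 days |
| Protocol 10.4 | Noted in the report, not used in the main analysis |

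Only 8.1b makes a test result depend on whether the death became known.

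**2. Size of the group at risk.** The plan gives no figure for this endpoint, so there is none to reproduce. The nearest source is protocol Table 2 (IRC002). Its category counts sum to 42 for plasma (21+7+6+7+0+1) and 43 for standard care (14+6+6+11+1+5), although the column header shows 45.

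- Still hospitalized at Day 28: 7/42 = 16.7% and 11/43 = 25.6%.
- Deceased: 1/42 = 2.4% and 5/43 = 11.6%.

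Apply these to the 135 subjects of protocol 12.2 at 2:1, that is 90 and 45:

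- In hospital at Day 28: 90 × 7/42 + 45 × 11/43 = 15.0 + 11.5 = 26.5, about 27 (19.6%).
- Deaths: 90 × 1/42 + 45 × 5/43 = 2.1 + 5.2 = 7.4, about 7.

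The group whose outcome is open is thus more than three times the expected number of deaths (26.5/7.4 = 3.6).

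**3. Later deaths.** The documents give no rate. If 5%, 10%, 20% or 30% of the 26.5 die later in the same admission (an assumption), that is 1.3, 2.7, 5.3 or 8.0 deaths, of which an unknown share would be reported.

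**4. Sensitivity of the test.** Two-sided Fisher p-values for illustrative counts (high-titer v low-titer):

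| Arm sizes | Deaths by Day 28 | p | One late high-titer death added | p |
|---|---|---|---|---|
| 100:50 | 2 v 6 | 0.017 | 3 v 6 | 0.061 |
| 90:45 | 2 v 5 | 0.041 | 3 v 5 | 0.12 |

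A late low-titer death works the other way: at 90:45, 2 v 6 gives 0.017. These counts show how fragile the test is. They do not predict the result.

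**5. The visit-based ends.** The Day 28 visit falls on Days 28–32 in protocol 6.3.10, on 28±3 in the SAP Table 1 row labelled per protocol (and 25–31 in SAP 7.1), and on Days 22–36 in the SAP analysis row. Under 8.1c, a Day 30 death counts if the assessment had not yet been done and does not count if it was done on Day 28. A Day 27 death after a Day 25 visit is lost from 28-day mortality. For durations, protocol 12.3 foresaw a Wilcoxon test adapted for censoring where needed, whereas SAP 10.4a names only Wilcoxon's test. With the plain test, a stay still running at a Day 28 visit ranks below one still running at a Day 32 visit.

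**The case against.** The strongest reply is that protocol 10.4 already keeps events after the Day 28 visit out of the main analysis, that death is an SAE, and that the SAP calls itself the final primary statistical analysis. The separate categories in SAP 10.3 also suggest that in-hospital death was meant within 28 days. This is a fair guess at the intention. However, 8.1b neither cites the rule nor clearly inherits it as a secondary endpoint, and the SAP restates a limit in 8.1c and 8.2 but not here.

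A reader might infer that none of the mortality and duration outcomes has an end, or that late deaths count by chance in all of them. The documents do not support that. SAP 8.1c and 10.4 state an end, though a subject-specific one, and 8.1c excludes later deaths. Log-rank and hazard-ratio methods tolerate censoring times that differ by a few days.

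A reader might also infer bias towards one arm. Nothing shows this: the trial is double-blind, and follow-up of unresolved SAEs makes late capture incomplete, not haphazard.

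On durations, the protocol's adapted Wilcoxon test would prevent ranking by visit date; the fault is that SAP 10.4a does not carry it over. Nor do the documents show how widely the visits of inpatients would scatter, since their data can be taken from the chart on the day.

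**Conclusion.** The point stands for 8.1b: one secondary mortality test has no cut-off and would combine complete with selectively captured deaths. About 27 of 135 subjects could be in the affected group against about 7 deaths, and one report can carry an illustrative p-value across 0.05. These figures are approximate. Table 2 gives disposition after the last discharge, not the initial one, so it may overstate initial stays still running. The 135 is a planning size that also allows for interim analyses. The later death rate is assumed.

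The visit-based ends are a smaller matter: a slight effect on the 8.1c log-rank test, and possible ranking by visit date in 10.4a. The Day 7 primary endpoint and its power are untouched. The change should be made, but nothing in the trial's main conclusion hangs on it.

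**What to change.** - **SAP 8.1b:** count only deaths in the initial hospitalization on or before Day 28 from randomization, and label the result in-hospital mortality through Day 28. Subjects still admitted and alive on that day count as alive. List later deaths outside the test.
- **SAP 8.1c:** censor administratively at Day 28 from randomization, or at last contact if earlier, including a Day 28 visit held before Day 28.
- **SAP 10.4:** truncate durations and incident use at Day 28 so that subjects still supported tie, or restore the censoring-adapted Wilcoxon test of protocol 12.3.
- **Windows:** reconcile 28–32, 28±3 and 22–36.

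The cost is SAP wording; dates of death, discharge, and start and stop of support are already collected (protocol 7.3.7, 12.4.2). Two drawbacks remain. A few known deaths on about Days 29–32 move from the test to the listing, and subjects whose Day 28 visit was early stay censored early unless their vital status on Day 28 is obtained.

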12 STATISTICAL CONSIDERATIONS

12.1 General Considerations

This is a randomized, double-blind study comparing high-titer versus low-titer anti-influenza immune plasma for the treatment of subjects hospitalized with severe influenza A infection. The primary analysis population for the evaluation of both efficacy and safety outcomes will include all subjects who have the

study plasma infusion started. This is an intention-to-treat analysis with the modification that subjects who are randomized but who do not have the study plasma infusion started will be excluded. Most subjects that do not receive plasma withdraw from the study early (Day 0-2 based in IRC002 data). Therefore, use of the modified intention-to-treat population is thought reasonable for this study. Supplementary intention-to-treat analyses including all randomized subjects for mortality, primary endpoint, and main secondary endpoints will be provided in the final analysis, though there may be limited follow-up data on many of the subjects who did not receive plasma.

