12.2 Sample Size and Power Considerations

The planned sample size for the trial is 150 subjects, randomized in an approximately 2:1 ratio to high-titer versus low-titer anti-influenza plasma. To evaluate the power of the study, the following assumptions were made:

- a. The primary analysis will compare the high-titer and low-titer plasmas using a proportional odds model and a two-sided Type I error rate of 0.05.
- b. It is anticipated that very few of these subjects will be randomized and not start study plasma infusion (and so be excluded from the primary analysis) or be lost to follow-up prior to Day 7 (and so have missing data for the primary endpoint). In addition, power is reduced slightly and hence the effective sample size is reduced by interim analyses reviewed by the DSMB. Conservatively, a 10% reduction in the total sample size from 150 to 135 subjects was made to allow for these issues.
- c. Data from the control arm of IRC002 for adults with influenza A infection, NEW score ≥ 3 , and duration of time from onset of symptoms of influenza to randomization ≤ 6 days, suggests the distribution of subjects in the low-titer arm for the primary endpoint shown in the following table:

Table 12: Anticipated Distribution of Subjects in the Ordinal Scale

| | Low-Titer Arm | High-Titer Arm | |
|---|----------------------|-----------------------|-----------|
| | (Based on IRC 002) | 80% Power | 90% Power |
| Died | 10% | 4.3% | 3.7% |
| In ICU | 35% | 20.4% | 18.4% |
| Non-ICU hospitalization, requiring supplemental oxygen | 25% | 23.6% | 22.6% |
| Non-ICU hospitalization, not requiring supplemental oxygen | 10% | 13.3% | 13.4% |
| Not hospitalized, but unable to resume normal activities | 5% | 7.9% | 8.2% |
| Not hospitalized, but with full resumption of normal activities | 15% | 30.6% | 33.7% |
| Proportional odds ratio comparing high titer to low titer | | 2.50 | 2.88 |

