Based on the above assumptions, the table also shows the type of true difference (assuming proportional odds) that would be detected with 80% or 90% power. For example, the study would have 80% power to detect a proportional odds ratio of 2.50. This is the odds ratio that arises when comparing the proportion not hospitalized and able to resume normal activities in the high-titer arm (30.6%) to that in the low-titer arm (15%). The proportional odds model assumes that the same odds ratio applies to the cumulative proportions moving up the ordinal scale: for example, for the proportion not hospitalized in the high-titer arm ($30.6+7.9=38.5\%$) to that in the low-titer arm ($15+5=20\%$); or for the proportion alive and not in an ICU in the high-titer arm ($30.6+7.9+13.3+23.6=75.4\%$) to that in the low-titer arm ($15+5+10+25=55\%$).

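### SAP 8.1b scores subjects with an unknown in-hospital outcome as survivors, and the censored 28-day mortality analysis in 8.1c has no ITT version

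*SAP*

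**What the plan says.** SAP 8.1b tabulates deaths during the initial hospitalization and tests them by Fisher's exact test. On the denominator it says: "The denominator for this analysis will be the number of subjects who have an infusion started (and so included in all analyses". It then adds a sensitivity analysis in the ITT population. SAP 4 does not define that population; Protocol 12.1 indicates all randomized subjects.

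Other parts of the two documents handle an unknown outcome differently:

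- SAP 1 leaves subjects with missing data out of percentages and, unless stated otherwise, restricts analyses to subjects with data. Item 8.1b states otherwise.
- SAP 10.3, which includes death during the initial stay as a disposition category, expects such cases: "showing also number with missing values (eg due to withdrawal of consent during initial hospitalization".
- SAP 10.2b (composite of death and hospitalization) shows a count of values missing through loss to follow-up.
- SAP 8.1c (28-day mortality) censors at the Day 28 evaluation, "or at date of last contact if lost to follow-up prior to Day 28 evaluation". It falls under the mITT heading of Section 8 and has no ITT version.

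Protocol 12.1 promises: "Supplementary intention-to-treat analyses including all randomized subjects for mortality, primary endpoint, and main secondary endpoints will be provided in the final analysis". On subjects never infused it says: "Most subjects that do not receive plasma withdraw from the study early (Day 0-2 based in IRC002 data". Protocol 4.4 states that subjects who withdraw consent fully are not contacted again.

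**The concern.** Fisher's test on a fixed denominator has two cells per arm, died and not died. A subject infused on Day 0 who withdraws fully from the ICU on Day 1 has an unknown outcome but falls in the second cell. In-hospital mortality is then understated in both arms, and the comparison is distorted if unknowns are more frequent in one arm. The reported p-value cannot show that anything is missing.

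The ITT repeat should show whether excluding never-infused subjects matters. As written, it adds back a group most of whom left within two days and counts nearly all of them as alive. Both rates fall, and almost no outcome information is gained. In 8.1c the same subjects could be kept without assuming survival, but the SAP asks for no ITT run there. In-hospital and 28-day mortality are both named secondary endpoints.

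**Working it through.** **The plan's own figure.** The documents give no power or precision for mortality. The only stated figure is for the primary ordinal endpoint: "the study would have 80% power to detect a proportional odds ratio of 2.50", with a "two-sided Type I error rate of 0.05". Using N = 3(A+1)²(z_α+z_β)² / [A (ln OR)² (1 − Σp̄³)] with A = 2 and the Table 12 distributions, N is 133, and power at 135 subjects is 80.7%. The figure reproduces and does not bear on this point.

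**Inputs for the illustration.**
- Death risks: 10% low-titer and 4.3% high-titer (Protocol Table 12, 80% power column). These are Day 7 rates, used in place of in-hospital risk.
- Size: 135 subjects (Protocol 12.2), "randomized in an approximately 2:1 ratio to high-titer versus low-titer anti-influenza plasma", so 90 and 45.
- Proportion w with unknown in-hospital outcome: not given in the documents, so assumed. Subjects with unknown outcome are given the same risk as the others.

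**Expected bias.** Reported risk = true risk × (1 − w).
- w = 0: OR = (0.043/0.957)/(0.10/0.90) = 0.404.
- w = 10% in both arms: risks 0.0387 and 0.090; OR = (0.0387/0.9613)/(0.090/0.910) = 0.407.
- Two unknowns per arm (2/90 and 2/45): risks 0.0420 and 0.0956; OR about 0.42.

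**Fisher's test on assumed counts.** Take 4 deaths in 90 (high) and 5 in 45 (low). The SAP result is 4.4% v 11.1%, p = 0.160, in every row.

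| Unknown, high/low (assumed) | Known outcome only | p if all high-titer unknowns died and no low-titer | p if the reverse |
|---|---|---|---|
| 2/2 | 4/88 v 5/43: 4.5% v 11.6%, p = 0.153 | 6/90 v 5/45: 0.506 | 4/90 v 7/45: 0.042 |
| 3/6 | 4/87 v 5/39: 4.6% v 12.8%, p = 0.134 | 7/90 v 5/45: 0.534 | 4/90 v 11/45: 0.001 |
| 10/5 | 4/80 v 5/40: 5.0% v 12.5%, p = 0.158 | 14/90 v 5/45: 0.604 | 4/90 v 10/45: 0.002 |

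**ITT version of 8.1b.** Add 10 high-titer and 5 low-titer never-infused subjects with no known death: 4/100 v 5/50, or 4.0% v 10.0%, p = 0.161. Both rates fall by a tenth and p hardly moves, which looks like robustness. Best/worst assignment of those 15 gives p = 0.607 (14/100 v 5/50) to 0.003 (4/100 v 10/50).

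**Which mortality analyses have an ITT version.** Item 8.1b does and 8.1c does not. SAP 10.1a and 10.2a have ITT sensitivity analyses of the ordinal scale, so ITT deaths are counted there as category 1, but neither tests mortality. SAP 5.1f only lists deaths among subjects not infused.

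**The case against.** The strongest case on the other side is that few subjects are affected. Protocol 12.2 expects very few to go without infusion or be lost before Day 7, and its 10% allowance also covers the interim looks. Protocol 4.4 asks withdrawing subjects to accept limited follow-up, including Day 28 vital status. Loss to follow-up is defined by failed telephone calls (Protocol 4.5), which mainly concerns discharged subjects. Full withdrawal before discharge is the main case left. Losses are also visible elsewhere, in SAP 5.1, 7.1 and 10.3. All of this stands, and it limits the size. It does not change how 8.1b scores the subjects who remain. SAP 1 allows best/worst scenarios, but only as an option and not tied to 8.1b.

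Items 8.1b and 10.3 would show the same deaths over different denominators. With both denominators stated, that is an inconsistency of method and less than a contradiction.

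The remedy is open to challenge too. Restricting to known outcomes drops subjects after randomization and assumes they resemble the rest. Never-infused subjects censored at Day 0-2 add almost no follow-up time, so an ITT run of 8.1c will nearly repeat the mITT result. Both objections are correct, which is why the bounds have to be mandatory.

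A reader might infer three stronger claims that the documents do not support:

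- **Withdrawal will be heavier in the control arm, as in IRC002.** Protocol 1.3.1 attributes that loss partly to subjects in an open trial not being chosen for treatment. This trial is blinded, with identically labelled plasma in both arms.
- **The 8.1b denominator could affect a DSMB decision on mortality.** The SAP covers the final analysis, and nothing ties 8.1b to the guideline in Protocol 10.8.
- **The choice of denominator could readily carry p across 0.05.** With 3 v 5 deaths it moves from 0.116 to 0.046, but only if 5 of 90 and 10 of 45 are unknown, far more than the protocol expects.

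**Conclusion.** The point holds on the text. Item 8.1b counts unknown in-hospital outcomes as survival, contrary to the SAP's general rule and to its handling of such subjects in 10.2b, 10.3 and 8.1c. The effect is most marked in the ITT version. Protocol 12.1 promises ITT for mortality without naming 28-day mortality; the SAP meets this only with the test least able to carry it, and 8.1c has no ITT run.

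The expected bias is probably small when losses are few and balanced: an odds ratio of 0.407 against 0.404 with 10% unknown per arm. The uncertainty that 8.1b hides can be larger, because deaths will be few: two unknowns per arm span p = 0.042 to 0.506 in the illustration. These sizes rest on assumed numbers of unknowns, assumed death counts and Day 7 rates standing in for in-hospital risk. The bounds are extreme by construction. This is worth correcting before analysis; it concerns secondary mortality analyses and does not touch the primary endpoint.

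**What to change.** In SAP 8.1b:

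1. Report unknown in-hospital outcome as a separate count by arm.
2. Base the percentage and Fisher's test on subjects with known outcome: died, discharged alive, or still in hospital at Day 28.
3. Make the best/worst assignment described in SAP 1 mandatory, for both the mITT and the ITT version.

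In SAP 8.1c, add an ITT run with never-infused subjects censored at last contact. State that early-censored subjects add little information, so that the bounds, and not that run alone, show how sensitive the result is to the mITT exclusion. Define the ITT population in SAP 4.

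The cost is a few lines of SAP text, the bounds, one extra run of an existing program and a slightly smaller denominator in 8.1b. No new data are needed.
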